#### 17.4.2.8.2 Analysis

The number of patients with hospital stays and their median, interquartile range and minimum and maximum total length of stay will be calculated for each treatment arm and each timeperiod. A Mann-Whitney test will be used to detect differences between treatment groups for each time-period of interest.

Two sensitivity analyses will be carried out: in each case where linear interpolation is needed (1) assume that all time spent hospitalised refers to the most probable time-period (so in the example assume that all 5 days recorded at 3.5 month visit occurred in the treatment phase; (2) assume that all time spent hospitalised refers to the least probable time-period (so in the example assume that all 5 days recorded at 3.5 month visit occurred during follow-up.

#### 17.4.2.9 Quality of life (CFQ)

The Cystic Fibrosis Questionnaire - Revised (CFQ-R) is a disease specific measure of health related quality of life (QoL) for children (aged 6 and over), adolescents and adults with cystic fibrosis. It covers nine quality of life domains, and three symptom scales.

The participant is asked to indicate their response to each question by ticking the most appropriate statement. Questions responses all have 4 possible responses. These are coded 1 to 4 from left to right or top to bottom.

There are three versions of the questionnaire:

- **CFQ-R Teen/Adult Version** (aged 14 and over) this is a self-administered questionnaire and consists of 50 questions. Participants are asked to complete the questionnaire alone in a quiet room.
- CFQ-R Child version (children aged 6-13 years) this questionnaire consists of 35 questions. For participants aged 12 and 13 years, it is a self-administered questionnaire and they are asked to complete the questionnaire alone in a quiet room. For participants aged 6 to 11 years, it is an interviewer-administered questionnaire whereby the research nurse reads out the questions to the participant and asks them to hold up coloured cards as their response to the questions.
- **CFQ-R Parent Version** (children aged 6-13 years) this is a self-administered proxy questionnaire to be completed by the parent or caregiver and consists of 44 questions.

See Table 3 below for details of which domains and symptom scales are measured in each questionnaire and how many questions relate to each.

NB There is no CFQ-R questionnaire available for children aged <6 years, therefore patients of this age are excluded from this analysis.

#### 17.4.2.9.1 Derivation

The CFQ-R data are collected within the questionnaire booklet CRFs: Adolescents & Adults; Children aged 12 or 13; Children aged 6-11; and Parent/care-giver.

There are four time-points for data collection: baseline,  $T_3$ ,  $T_{15}$  and (if applicable)  $T_{24}$ . For each time-point, a total of 23 domain response variables will be calculated using the scoring system developed for the CFQ [12]. 8 of these are derived by combining data from the two self-completed questionnaires; 4 of these relate only to teens/adults (health perceptions, role functioning, vitality and weight); 11 are derived from the parent/carer questionnaire.

#### Form prepared: 20/06/2018 v1.0 for TORPEDO-CF Study

Page 37 of 47

A handful of questions' scores are reversed at the derivation stage: these are indicated in the scoring system guidelines. All response variables are derived by finding the mean score of question responses within a domain, subtracting 1, and then multiplying by 3/100 to obtain a standardised 0-100 scale.

A categorical time-point variable will be created with values 0,1,2,3 or 4 denoting whether the response is measured at baseline,  $T_3$ ,  $T_{15}$  or  $T_{24}$  resp.

Missing data: the guidelines suggest that where less than half of questions have been answered within a domain, then the score for the domain will be treated as missing.

Table 3: Number of questions asked, corresponding to each domain/scale within ea	ach
questionnaire	

	Self-r		
Domain/Scale	Teen/Adult (>13)	Child (6-13)	Parent/Carer
Physical functioning	8	6	8
Role/school functioning	4	-	4
Vitality	4	-	5
Emotional functioning	5	8	5
Social functioning	6	7	-
Body Image	3	3	3
Eating problems	3	3	2
Treatment Burden	3	3	3
Health perceptions	3	-	3
Weight	1	-	1
Respiratory symptoms	7	4	7
Digestive symptoms	3	1	3
Total number of questions	50	35	44

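### The CFQ-R scoring formula inverts its scaling factor: multiplying by 3/100 gives scores from 0 to 0.09, not the stated 0 to 100

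*SAP*

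**What the plan says.** SAP section 17.4.2.9 describes the CFQ-R items: "Questions responses all have 4 possible responses". On the coding it says "These are coded 1 to 4 from left to right or top to bottom".

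Section 17.4.2.9.1 then gives the scoring rule. It first deals with reversed items: "A handful of questions' scores are reversed at the derivation stage: these are indicated in the scoring system guidelines". It continues: "All response variables are derived by finding the mean score of question responses within a domain", then "subtracting 1, and then multiplying by 3/100 to obtain a standardised 0-100 scale".

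The rule covers 23 variables at each time point: 8 that combine the two self-completed questionnaires, 4 for teens and adults only, and 11 from the parent or carer questionnaire (8 + 4 + 11 = 23). The same section points to a published scoring system (SAP reference 12) as the basis for the scores. Section 17.4.2.9.2 takes the scores into a repeated-measures mixed model for each domain. It reports group means with SDs, the modelled difference at T15 with its 95% CI, a p-value, and a plot of means with standard errors.

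**The concern.** The rule and its stated result cannot both be right. With items coded 1 to 4, the written multiplier shrinks the score to a small fraction of one unit, while the same sentence says the scale runs from 0 to 100.

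This is the only explicit scoring formula in the SAP, and it applies to every CFQ-R variable. A programmer who follows it literally produces quality-of-life results that cannot be read on the promised scale. A validator who checks a correct program against the SAP finds a mismatch.

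**Working it through.** **Inputs**

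- Item codes 1, 2, 3, 4 (SAP 17.4.2.9).
- Domain summary: the mean of the item responses, so it lies between 1 and 4 (SAP 17.4.2.9.1).
- Written factor 3/100 and stated target 0 to 100 (SAP 17.4.2.9.1).
- Assumption: reversed items are reversed within the same codes (5 minus the value), which leaves the range at 1 to 4.

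**Trying to reproduce the stated scale**

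Score = (domain mean − 1) × factor.

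| Domain mean | Mean − 1 | × 3/100 (as written) | × 100/3 |
|---|---|---|---|
| 1 | 0 | 0 | 0 |
| 2 | 1 | 0.03 | 33.3 |
| 2.5 | 1.5 | 0.045 | 50 |
| 3 | 2 | 0.06 | 66.7 |
| 4 | 3 | 0.09 | 100 |

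The written factor does not reproduce the 0 to 100 scale. The inverted factor reproduces it exactly. Dividing by 3/100 would also work, since that is the same as multiplying by 100/3, but the text says to multiply.

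**Size of the error**

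Ratio of the two factors: (100/3) / (3/100) = 10,000/9 = 1,111.1. Equivalently, the written rule returns 0.0009 times the intended score. A 10-point difference becomes 10 × 0.0009 = 0.009.

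**What does and does not change in the model**

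Let c = 0.0009. The outcome and the baseline covariate are both multiplied by c. The treatment estimate and its standard error are then each multiplied by c, so their ratio, the p-value and the sign are unchanged. Group means, SDs, the T15 difference, its confidence limits and the plotted means and standard errors are all multiplied by c.

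**Other text that might correct it**

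No other section gives a different formula. The change control table lists a version 2.0 revision to the CFQ analysis (17.4.2.9.2) but none to the derivation (17.4.2.9.1), so the log records no correction.

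**The case against.** The strongest reply is that this is a slip of the pen that the document itself exposes. The sentence names the intended scale, the section refers to a published scoring system, and SAP section 5 says the analysis programs will be tested and validated. A score that cannot exceed 0.09 on a declared 0 to 100 scale would probably be noticed. The error is also a known constant, so it can be undone. It leaves inference unchanged and concerns one of 16 secondary outcomes. The SAP sets no CFQ-R cut-off that would be misapplied, and T24 applies to only some patients.

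Most of this stands. The 1,111-fold error arises only if the fraction is programmed literally, and nothing in the SAP shows that it would be. The primary outcome is untouched.

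None of it makes the formula right. The reference to an outside scoring system leaves the programmer with two instructions, one of which cannot give the stated scale. Validation against the written SAP would favour the wrong one. The error is fully reversible only from unrounded values. The SAP fixes no precision for CFQ-R results, but if they were printed to two decimals (the finest used in SAP Table 1), one printed step of 0.01 would correspond to 0.01/0.0009 = 11.1 points on the intended scale.

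**Conclusion.** The formula is wrong as written. The SAP's own item coding and stated target scale are enough to show it, and no outside source is needed. Taken literally, it yields scores from 0 to 0.09 and makes every CFQ-R mean, SD, difference and confidence limit 1,111 times too small, across 23 domain variables at up to four time points (T24 only where applicable). P-values and directions of effect are unaffected.

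The range rests on the 1 to 4 coding and on reversal staying within those codes. The effect on reported results rests on the formula being programmed as printed. It should be corrected because the error is certain, it reaches every quality-of-life estimate, and these estimates are what a reader would use to judge clinical size. It does not threaten the trial's main conclusion.

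**What to change.** In SAP section 17.4.2.9.1, replace 3/100 with 100/3, so that score = (domain mean − 1) × 100/3, applied after the item reversal already described there. Record the change in the change control table.

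Check the scoring program with two test cases: a domain mean of 1 must return 0, and a domain mean of 4 must return 100. If any CFQ-R output has already been produced, confirm which factor was used.

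The cost is one line in the SAP and, if the program copied the fraction, one line of code. No data, sample size or design decision is involved.

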#### 17.4.2.9.2 Analysis

For each of the 23 domains:

A mixed-effects model for repeated measures will be fitted, with an unstructured covariance matrix. The baseline measurement of the domain will be fitted as a covariate along with *Form prepared:* 20/06/2018 v1.0 *for TORPEDO-CF Study* 

treatment group, time-point as a categorical variable and an interaction term (treatment group\*time). The following will be reported: mean (SD) for each treatment group; mean (95% CI) difference between treatment groups at  $T_{15}$  (derived from the model); and a p-value of the treatment effect. A plot of mean (SE) for each time-point, by treatment group will be presented.

#### 17.4.2.10 Utility (EQ-5D)

#### 17.4.2.10.1 Derivation

The derivation of this outcome will be described in the health economics analysis plan.

#### 17.4.2.10.2 Analysis

The analysis of this outcome will be described in the health economics analysis plan.

#### 17.4.2.11 Adverse events

See Section 20 below.

## 17.4.2.12 Other sputum/cough Microbiology (Methicillin resistant *Staphylococcus aureus* (MRSA), *Burkholderia cepacia* complex, Aspergillus, Candida Infection)

#### 17.4.2.12.1 Derivation

All microorganisms detected at each visit are recorded in the CRF: *Microbiology*. MRSA, *Burkholderia cepacia* complex (BC) and Candida are listed in the CRF explicitly and are identified by the variables MBOC3C='Yes', MBOC4C='Yes' and MBOC2C='Yes' respectively. All other detected organisms (other than *P.aeruginosa*) are recorded in the variable MBOCT. The date of detection of a microorganism is recorded by the variable MBDSTD.

For the time-period: 1st 15 months post randomisation, the following four outcome variables will be derived:

- (1) MRSA = 1 if there is at least one instances where MBOC3C='Yes' and date of detection < 15 months post randomisation;
  - = 0 otherwise
- (2) BC = 1 if there is at least one instances where MBOC4C='Yes' and date of detection < 15 months post randomisation;
  - = 0 otherwise
- (3) Candida = 1 if there is at least one instances where MBOC2C='Yes' and date of detection < 15 months post randomisation;
  - = 0 otherwise
- (4) Asp = 1 if there is at least one instances where MBOCT contains 'Aspergillus' and date of detection < 15 months post randomisation;
  - = 0 otherwise

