#### 8.9 Schedule of assessments

Table 3 in Section 7 of the protocol outlines the schedule of assessments.

Note that for the purpose of this trial, a 'month' is defined as 28 days. Visits should have occurred as follows:

	Scheduled study visit	Time after treatment start
T 3	3 months	12 weeks
$T_6$	6 months	24 weeks
T 9	9 months	36 weeks
T 12	12 months	48 weeks
T 15	15 months	60 weeks
T 18	18 months	72 weeks
T 21	21 months	84 weeks
T 24	24 months	96 weeks

Due to large numbers of visits occurring outside of appropriate visit windows and not consistently being captured on scheduled or unscheduled visit CRFs; where outcomes refer to specific time points, data will be included based on dates of assessments rather than CRF names. For an assessment to be associated with a particular time-point it must have occurred within 1 week either side of the expected visit date, apart from  $T_{15}$  which may be minus 1 week or plus 2 weeks of the expected visit date.

Not all patients were followed up after  $T_{15}$ .  $T_{18}$ ,  $T_{21}$  and  $T_{24}$  were proposed in the protocol up to and including version 7. Patients randomised after 1st January 2016 were required to complete up to and including  $T_{15}$  only.

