#### Table 1: Continuous baseline variables to be reported

Variable	Unit of	Precision	CRF where data are recorded
	measurement	(decimal	
		places)	
BMI z-score	-	2	Derived from height and weight data
(participants			contained in Baseline CRF. See Section
registered at			17.4.2.5.1 below for derivation.
paediatric centres)			
BMI	m/kg²	1	Derived from height and weight data
(participants			contained in Baseline CRF. See Section
registered at centres			17.4.2.5.1 below for derivation.
treating adults)			
Time from	days	0	Baseline – Section 3: date of report
Pseudomonas			confirming P.aeruginosa isolation.
isolation to treatment			Treatment CRFs, Section 1: date started
initiation*			treatment / date started.
%predicted FEV1	litres	2	Raw FEV1 data contained in Baseline
(participants aged 5 or			CRF. See Section 17.4.2.3.1 below for
older only)			derivation.
%predicted FVC	litres	2	Raw FVC data contained in Baseline
(participants aged 5 or			CRF. See Section 17.4.2.3.1 below for
older only)			derivation.
%predicted FVC 25-75	litres	2	Raw FVC data contained in Baseline
(participants aged 5 or			CRF. See Section 17.4.2.3.1 below for
older only)			derivation.
O 2 Saturation	%	2	Baseline

\*Calculated as the number of days from the date of report confirming *P.aeruginosa* isolation to the date of treatment commencement.

Variable	Categories	CRF where data are recorded
Age-group (a)	Infants and toddlers (28 days – 23 mths)	Derived from continuous value obtained from Baseline CRF
	Children (2-11 yrs)	
	Adolescents (12-17 yrs)	
	Adult: 18-64 yrs	
	Elderly adult: ≥ 65 yrs	
Gender	Male	Baseline
	Female	
Pseudomonas	Naïve	Baseline
status	Free	
Other	Candida	Microbiology (see Section
microorganisms	MRSA	17.4.2.12.1 below for derivation)
detected	Burkholderia cepacia	
	Aspergillus	
	Other organisms	
Genotype	F508/F508	Baseline
	F508/other	
	F508/unknown	
	other/other	
	Diagnosis not based on genetics	
Pulmonary	Yes	Baseline (see Section 17.4.2.6.1
Exacerbation	No	below for derivation)

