#### 17.4.1.1 Derivation

The CRF: *Microbiology Form* captures information on samples taken at all attended visits (scheduled and unscheduled). The variable MBDSTD gives the date the sample was taken, and the variable MBOC6C indicates that *P. aeruginosa* was cultured if it is selected (MBOC6C = "Pseudomonas aeruginosa").

Success: If there is no record of *P. aeruginosa* on a patient's microbiology CRF between 3 months and 15 months after treatment commencement.

Failure: If there is at least one record of *P. aeruginosa* on a patient's microbiology CRF between 3 months and 15 months after treatment commencement.

Any positive samp	Outcome		
<3 months	3-15 months	>15 months	
×	×	×	Success
×	×	✓	Success
✓	×	×	Success
✓	×	✓	Success
×	$\checkmark$	×	Fail
×	$\checkmark$	✓	Fail
✓	$\checkmark$	×	Fail
✓	$\checkmark$	$\checkmark$	Fail

To determine if a patient has eradicated *P. Aeruginosa* at 3 months, they must have a sample within 28 days either side of the expected 3 month visit date (treatment commencement date + 84 days) which is at least 2 days after the last date of any anti-pseudomonal treatment.

To determine if a patient has remained *P. Aeruginosa* free at 15 months, they must have either a positive sample within the primary outcome window (3-15 months) or they must have a sample within 28 days either side of the expected 15 month visit date (treatment commencement date + 420 days). Patients who have not regrown *P. Aeruginosa* and do not have a sample within the 15 month window (defined above) will not be included in the primary analysis. If a patient is withdrawn before 15 months of follow-up is completed, they will only be included in the primary outcome analysis if they have failed. If there is no evidence that they have failed prior to being withdrawn they will not be included in the primary analysis.

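### Other microbiology (SAP 17.4.2.12.1): the strict cut-off counted from randomisation always excludes an on-time T15 culture and scores a first positive there as negative

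*SAP*

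**What the plan says.** Section 17.4.2.12.1 takes its data from the Microbiology form: "All microorganisms detected at each visit are recorded in the CRF". It then sets the period: "For the time-period: 1 st 15 months post randomisation, the following four outcome variables will be derived". Each of the four variables equals 1 if at least one positive culture has "date of detection < 15 months post randomisation", and 0 otherwise. The four conditions contain no lower date limit.

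Section 8.9 states that "for the purpose of this trial, a 'month' is defined as 28 days" and places T15 at 60 weeks after treatment start. For T15 the general assessment window is one "which may be minus 1 week or plus 2 weeks of the expected visit date". Section 17.4.1.1, for the primary outcome, uses the "expected 15 month visit date (treatment commencement date + 420 days".

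The analysis section for this outcome (17.4.2.12.2) reports relative risks with confidence intervals and tests. It also tabulates positives by 15 months and, for those followed that far, by T24. In Table 2 of Section 17.2, the baseline row for other organisms sends the reader to "17.4.2.12.1 below for derivation".

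**The concern.** Two features of one condition combine: the inequality is strict, and the clock starts at randomisation although the visit schedule starts at treatment commencement. The last planned culture of a 15-month outcome then falls outside the outcome's own period. Because the alternative to a counted positive is 0 rather than missing, a positive at that culture is not merely unused; it turns a patient with the organism into one without it.

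The rule also disagrees with its surroundings. Section 17.4.2.12.2 describes the same outcome as positives by 15 months, which reads as inclusive. Re-infection with a different genotype (17.4.2.2.1), hospital admission (17.4.2.7.1) and carer burden (17.4.2.15.1) all run up to and including T15. The primary outcome reads the same form and the same sample-date variable, and accepts a T15 sample up to 28 days either side of the due date. One T15 specimen can therefore count for *P. aeruginosa* and be ignored for MRSA.

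This is a listed secondary outcome (9.2, item 12) with formal comparisons, so two programmers reading different sentences could report different counts.

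**Working it through.** The SAP gives no figure to reproduce here; the check is date arithmetic.

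**Inputs**
- Month = 28 days (8.9), so the cut-off is 15 × 28 = 420 days from randomisation, exclusive.
- T15 due date = 60 × 7 = 420 days from treatment commencement (8.9, 17.4.1.1).
- General T15 window = 420 − 7 to 420 + 14, i.e. days 413 to 434 from treatment commencement: 434 − 413 + 1 = 22 days.
- Lag *g* = days from randomisation to treatment commencement, *g* ≥ 0. The SAP treats the two dates as different origins (19.2.1) but does not give the lag. I assume 0 to 21 days for illustration; 14.1 lists inability to start treatment within 21 days of the positive report as a reason for ineligibility.

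**On-time culture.** It falls on day 420 + *g* from randomisation. The rule needs 420 + *g* < 420, which is false for every *g* ≥ 0.

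**Whole T15 window.** A culture on day *d* from treatment commencement passes if *d* + *g* < 420, i.e. *d* ≤ 419 − *g*. The number of passing days is max(0, 419 − *g* − 413 + 1) = max(0, 7 − *g*). With `≤` in place of `<` it is max(0, 8 − *g*).

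| Lag *g* (assumed) | On-time T15, day from randomisation | Window days passing, `<` | Window days passing, `≤` |
|---|---|---|---|
| 0 | 420 | 7 of 22 | 8 of 22 |
| 1 | 421 | 6 of 22 | 7 of 22 |
| 3 | 423 | 4 of 22 | 5 of 22 |
| 7 | 427 | 0 of 22 | 1 of 22 |
| 14 | 434 | 0 of 22 | 0 of 22 |
| 21 | 441 | 0 of 22 | 0 of 22 |

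Changing the sign alone rescues the on-time culture only when *g* = 0. Counting from treatment commencement and closing the window at day 434 admits 22 of 22 days whatever the lag.

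**If randomisation is programmed as treatment start.** Section 17.4.2.1.1 labels its origin as randomisation but maps it to the same variables that 19.2.2.1 labels as first treatment. If that mapping were reused here, *g* would be 0 by construction. The first row applies, and the on-time culture is still excluded.

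**Lower limit.** Any culture dated on or before randomisation satisfies a condition of being earlier than day 420, so the four conditions taken alone would admit the baseline sample. The sentence that introduces them does start the period at randomisation; that start is simply not carried into the conditions.

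**The case against.** **Calendar months.** Fifteen calendar months are 15 × 365.25/12 = 456.6 days, and all 22 window days would then pass for lags of 0 to 21 days. But Section 8.9 defines the month as 28 days for the whole trial, so this reading contradicts the SAP.

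**Only the last visit is touched.** This stands. Earlier scheduled and unscheduled cultures remain. The by-T24 table recovers T15 positives for patients followed that far, and the by-15-months table may do so if programmed inclusively. That limits the damage but leaves the main comparison wrong as written.

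**Bias towards 1.** A reader might infer that losing the T15 culture pulls the relative risks towards 1. The SAP does not support that. The same rule shortens observation in both arms. With low event rates and a constant rate ratio, the relative risk is essentially unchanged; if an effect wanes after treatment, truncation can move it away from 1. The SAP gives no lag by arm from which to argue otherwise.

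**Baseline carriage.** A reader might also infer that the outcome has no start, so that baseline carriage is counted as new infection and dilutes the effect. This goes too far, for three reasons:
- The introductory sentence states a start.
- The Table 2 cross-reference is most naturally a pointer to the organism variables, since a 15-month window cannot define a baseline characteristic.
- The planned outcome is at least one positive result; the SAP never calls it new acquisition, and any-positive is a legitimate choice in a randomised comparison.

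Dilution can be illustrated with 20% carriage in both arms and acquisition of 10% v 20% among the rest: 0.20 + 0.80 × 0.10 = 0.28 and 0.20 + 0.80 × 0.20 = 0.36, ratio 0.78 rather than 0.50. Those rates are invented. Moreover, carriers who are positive again after randomisation count whether or not the baseline sample is excluded, so the cause would be the absence of a rule for baseline-positive patients, not a missing start date.

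**Conclusion.** The upper bound is wrong as written. Under the SAP's own month and schedule, an on-time T15 culture is excluded at every lag of 0 or more, and a first positive there is scored as negative. At most 7 of the 22 T15 window days survive, and none once the lag reaches 7 days.

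These are days of the window, not shares of patients. A reader might infer that most patients lose their T15 culture, but that depends on the lag and on the spread of visit dates, neither of which the SAP gives. The supported consequence is lost events and precision in four tested comparisons, together with an internal conflict over what 15 months includes.

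The missing lower limit is a smaller matter: a stated start that has not been written into the conditions. The point is worth correcting before analysis, but it concerns a secondary outcome and does not touch the primary result.

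**What to change.** In Section 17.4.2.12.1:

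1. Count from treatment commencement, and include samples up to and including the T15 sample within the Section 8.9 window (day 413 to day 434). Use this general window rather than the 28-day allowance, which the SAP sets specifically for the primary outcome. Replacing `<` by `≤` is not enough if there is any lag.
2. Write the start of the period into all four conditions and say explicitly that the baseline sample is excluded, including one dated on the day the period opens.
3. Apply the same bounds to the by-15-months table in 17.4.2.12.2. Add a line to Table 2 saying that its cross-reference covers the organism variables only.

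Optionally, add a supplementary table restricted to patients negative for the organism at baseline, because persisting carriage otherwise counts as a positive. This is an addition, not a correction.

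Items 1 to 3 cost a few lines of SAP text and two date conditions in the derivation program; no new data are needed. The optional table is one further output per organism.
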